8.3. Concomitant Medications

8.3.1. Permitted Medications and Treatments

Therapy considered necessary for the subject's welfare that will not interfere with the evaluation of the study medication may be given at the discretion of the Investigator. If there is any question as to whether the medication may interfere, the Investigator should contact the Medical Monitor or Sponsor. Whenever possible, medications should be administered in dosages that remain constant throughout the study duration. Note: Artificial tear use is permitted prior to and during the study period as needed provided the use is not required for severe dry eye disease. Artificial tears should not be instilled within 10 minutes of administration of study medication.

8.4. Treatment Compliance

Treatment compliance will be monitored by subject-reported missed doses assessed at each treatment visit (Visit 4/Day 15, Visit 5/Day 42, and Visit 6/Day 84) via response to the Missed Doses Log. Subjects will be asked to log if they have missed any doses since the previous visit, and if so, the date of missed dose, which dose was missed (AM and/or PM), which eye was not dosed (right, left, both), and the reason for the missed dose. These data will be analyzed to determine an estimate of compliance over the duration of the study.

8.4.1. Prohibited Medications

The Medical Monitor should be notified before prohibited medication or therapy is administered unless the safety of the subject requires immediate action. The decision to administer a prohibited medication or therapy should be done with the safety of the subject as the primary consideration. The Medical Monitor MUST be contacted to determine whether the subject should continue with study medication.

Prohibited medications and therapies are summarized in Table 3 and specific details are found in the Study Manual.

8.5. Study Medication Materials and Management

8.5.1. Packaging and Labeling

Study medication will be packaged and labeled at a central packaging facility. Study sites will utilize the IWRS to assign kits to subjects. Each kit has 3 boxes (subkits). Contents of the boxes

(subkits) will differ depending upon treatment allocation (either 5 mL multidose bottles or 10 mL multidose bottles).

- Box 1, dispensed at Visit 3/Qualification/Baseline, includes either 1 bottle (5 mL) of BTQ-1901-A, BTQ-1901-B, BTQ-1902 OR 1 bottle of timolol 0.5% (10 mL)
- Box 2, dispensed at Visit 4/Day 15, includes either 2 bottles (5 mL each) of BTQ-1901-A, BTQ-1901-B, BTQ-1902 OR 2 bottles of timolol 0.5% (10 mL)
- Box 3, dispensed at Visit 5/Day 42, includes either 3 bottles (5 mL each) of BTQ-1901-A, BTQ-1901-B, BTQ-1902 OR 3 bottles of timolol 0.5% (10 mL)

8.5.2. Storage and Administration

Study medication must be stored at room temperature, 15°C - 25°C, or 59°F - 77°F, under temperature monitored conditions. Subjects should be instructed not to store or place the study medication where it can be exposed to extreme temperatures (e.g., refrigeration or leaving it in a hot car) or light.

An unmasked staff member *not* involved in performing study endpoint-related procedures will instruct the subject on proper instillation technique and dispense the first study medication kit at Visit 3/Qualification/Baseline. At each study visit during the treatment period (Visit 4/Day 15, Visit 5/Day 42, and Visit 6/Day 84) the subject (or caregiver, if the subject is not able to self-administer the medication) will administer the morning dose of study medication at the study site, instilling 1 drop in each eye. Before administering the eye drops, the hands should be washed. The steps described in detail in the Subject Dosing and Storage Instructions will be followed.

Each day of dosing, the subject will administer one drop to each eye BID (morning and evening).

8.5.3. Study Medication Accountability

An unmasked staff member *not* involved in performing endpoint procedures will maintain full accountability records for the study medication and will be responsible for recording the receipt, dispensing, and return of all supplies of the study medication using the inventories supplied by the Sponsor. At each visit subsequent to Visit 3/Qualification/Baseline (i.e., Visit 4/Day 15, Visit 5/Day 42, and Visit 6/Day 84) all bottles that were dispensed at the previous visit (empty, used, or unused) should be returned to the site in the kit. At Visits 4 and 5, study medication accountability procedures will be conducted, and new study medication kits will be dispensed for the next study period. At Visit 6 all study medication materials will be returned to the study site, and final study medication accountability will be conducted. Visit 6 will be the last day of study treatment; no further study medication will be dispensed at this visit. The monitor will review dispensing and study medication accountability records at the completion of the study and note any discrepancies. All investigational study medication must be stored in a secure facility with limited access.

9. STUDY ASSESSMENTS

Prior to entry into the study or initiation of any study-related procedures, the subject must read, sign, and date the current Institutional Review Board (IRB)-approved version of the informed consent form (ICF). A full discussion of informed consent is presented in Section 13.3. Ophthalmic procedures should be performed in the order specified in Table 2.

9.1. Demographic and Background Characteristics

9.1.1. Demographic/Medical History

A complete medical history will be obtained from each subject. Demographic information including date of birth, gender, race, ethnicity, iris color, and date of informed consent will be recorded.

9.1.2. Concomitant Medications History

All concomitant medications (prescription and over-the-counter [OTC]) taken at Visit 1/Screening and for 90 days prior to Visit 1 and throughout the course of the study will be recorded in the Concomitant Medications page of the eCRF. Information regarding the dates of first and last dose, site of dosing (e.g., right eye, left eye, both eyes [OU], systemic), and the reason the concomitant medication is being taken must be recorded in the eCRF. When a concomitant medication has been taken at a stable dose for longer than 6 months, an estimation of the year of the start date is adequate. Standard procedural medications will not be captured in the eCRF but are recorded on a standard procedural medication log provided by the CRO.

9.1.3. Ophthalmic History and Ophthalmic Intervention History

Clinically significant ophthalmic history and ophthalmic intervention history will be documented and will include any clinically significant previously diagnosed ophthalmic abnormalities and ocular surgeries, including laser procedures.

9.1.4. Urine Pregnancy Test

A urine pregnancy test will be performed for females of childbearing potential at Visit 1/Screening, Visit 3/Qualification/Baseline, and Visit 6 or Early Discontinuation Visit.

9.2. Efficacy Assessment

The efficacy of BTQ-1901-A (nebivolol 0.5%), BTQ-1901-B (nebivolol 1.0%) or BTQ-1902 (timolol 0.5%) ophthalmic suspensions will be compared to the active comparator (timolol 0.5% ophthalmic solution) as measured by mean IOP values in the study eye at each time point at each of the Visit 4/Day 15, Visit 5/Day 42, and Visit 6/Day 84 visits (ie, a total of 9 between-group comparisons).

9.2.1. Intraocular Pressure

Intraocular pressure will be measured utilizing a calibrated Goldmann tonometer and using the standard of care. NOTE: For 3 through 6, IOP measurements must be made within 30 minutes of the protocol-specified time points (8:00 AM, 10:00 AM, and 4:00 PM for Visit 3 and 8:00

AM, 2 hours after study medication dosing at the clinical site [~10:00 AM], and 4:00 PM for Visits 4, 5, and 6). For any given subject, IOP should be measured with a calibrated tonometer and by the same Investigator/designee, if possible, throughout the study who will be masked to the readout of the tonometer, which will be read and entered into the source documentation (whether electronic or paper) by a second staff member once the Investigator/designee reaches the correct applanation effect in the slit lamp. Two consecutive IOP measurements of each eye will be performed. If the 2 measurements differ by more than 2 mm Hg, a third measurement will be taken. Consult the Study Manual for specific details.

9.3. Pharmacokinetic Assessments

Plasma concentration will be measured in a subset of 40 subjects; blood samples will be collected 2 hours (\pm 30 minutes) after study medication dosing at the clinical site at Visit 4/Day 15 and Visit 6/Day 84. Consult the Study Manual for specific details.

9.4. Safety Assessments

Safety will be assessed at each visit by LogMAR VA, biomicroscopy, resting heart rate (HR)/blood pressure (BP), and AE collection. Ophthalmoscopy/dilated fundus examination and VF testing will be performed at Visit 1/Screening and Visit 6/Day 84. Safety/tolerability assessments at each visit will include grading of conjunctival hyperemia by the Investigator and subjective assessment of comfort/tolerability data by the subject. Ophthalmic assessments should be performed in the order in which they appear in the Schedule of Procedures (Table 2).

9.4.1. Visual Acuity

Best corrected visual acuity measurement will be performed in each eye at all study visits with the logMAR eye chart. Consult the Study Manual for specific details.

9.4.2. Biomicroscopy

A slit-lamp examination will be conducted at each study visit to assess the anterior ocular structures. Abnormalities will be documented as abnormal, non-clinically significant (NCS) or abnormal, clinically significant (CS). Consult the Study Manual for specific details.

9.4.3. Grading of Conjunctival Hyperemia

Conjunctival hyperemia will be graded using the McMonnies photographic scale (McMonnies and Chapman, 1987a; McMonnies and Chapman, 1987b). Please note that this scale was designed for contact lens wearers but validated for non-contact lens wearers (McMonnies and Ho, 1991). Consult the Study Manual for specific details.

9.4.4. Vital Signs

Blood pressure and HR will be measured after at least 5 minutes rest in the sitting position. Vital signs may be repeated once, after at least an additional 5 minutes rest in the seated position, if they are out of range. Consult the Study Manual for specific details.

9.4.5. Ophthalmoscopy/Dilated Fundoscopy

Ophthalmoscopy/dilated fundoscopy will be conducted, and the structures will be graded as normal or abnormal, NCS, or abnormal, CS. Consult the Study Manual for specific details.

9.4.6. Visual Field Testing

Automated perimetry will be performed at Visit 1/Screening and Visit 6/Day 84. The site should perform the automated perimetry assessments following the investigator's standard practices. If the VF performed at or within 90 days prior to Visit 1 does not meet study required parameters, it may be repeated (test should be prior to randomization at Visit 3/Qualification/Baseline/Day 1).

The preferred equipment for the VF is the Humphrey Perimeter using the full threshold 24-2 test with the SITA Standard or SITA Fast strategy. The same strategy used for the initial test should be used for any subsequent VF test. Visual field results should be reliable. Subjects with a functionally significant VF loss, defined as mean deviation greater than -12 dB or a central fixation point less than 5 dB in either eye, are excluded from the study. Other equipment may be used after approval by the Sponsor. Consult the Study Manual for specific details.

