- 2. Able to administer or have a caregiver accurately administer an eye drop.
- 3. 18 years of age or older, male, or female.
- 4. Have POAG or OHT in both eyes that requires therapy for IOP and is adequately controlled, in the opinion of the Investigator, on no more than 2 ocular hypotensive medications (fixed dose combinations count as 2 medications). Subjects with OHT on no ocular hypotensive medication are acceptable. Presence of POAG in one eye and OHT in the fellow eye is acceptable.
- 5. Able, in the opinion of the Investigator, to safely discontinue use of ocular hypotensive medications, if applicable, and undergo the appropriate required washout period for ocular hypotensive medications prior to Visit 3/Qualification/Baseline.
- 6. At Visit 3/Qualification/Baseline, at least one eye must have unmedicated (post washout) IOP ≥ 22 and ≤ 34 mm Hg at 8:00 AM, and ≥ 18 and ≤ 34 mm Hg at 10:00 AM and 4:00 PM (in the same eye[s] qualifying at the 8:00 AM time point). The IOP must be at least 22 mm Hg at each consecutive measurement at the 8:00 AM time point.
- No significant visual field (VF) loss, defined as a mean deviation in either eye greater than

 12 dB or a central point of fixation < 5 dB in either eye. If the VF performed at or within
 90 days prior to Visit 1 does not meet study required parameters, it may be repeated (test
 should be prior to randomization at Visit 3/Qualification/Baseline).

Inclusion Criteria (continued):

- 8. Best corrected visual acuity (BCVA) of +0.6 logMAR or better in both eyes at Visit 1/Screening and Visit 3/Qualification/Baseline.
- 9. Central corneal thickness \ge 480 and \le 600 μ m in both eyes. Pachymetry within 90 days prior to Screening is acceptable.
- 10. Shaffer gonioscopic grade \geq 3 (in at least 3 quadrants) in both eyes. Gonioscopy within 90 days prior to randomization is acceptable.
- 11. Female subjects must be 1-year postmenopausal, surgically sterilized (total hysterectomy, bilateral oophorectomy or bilateral tubal ligation > 90 days prior to Visit 1/Screening), or women of childbearing potential with a negative urine pregnancy test at Visit 1/Screening and Visit 3/Qualification/Baseline who are not breastfeeding or planning a pregnancy during the study. Women of childbearing potential must use an acceptable form of contraception throughout the study. Acceptable methods include the use of at least one of the following:
 - Intrauterine (IUD) device,

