7. SELECTION AND WITHDRAWAL OF SUBJECTS

7.1. Inclusion Criteria

- 1. Willing and able to understand and sign an informed consent form prior to any study related procedures.
- 2. Able to administer or have a caregiver accurately administer an eye drop.
- 3. 18 years of age or older, male, or female.
- 4. Have POAG or OHT in both eyes that requires therapy for IOP and is adequately controlled, in the opinion of the Investigator, on no more than 2 ocular hypotensive medications (fixed dose combinations count as 2 medications). Subjects with OHT on no ocular hypotensive medication are acceptable. Presence of POAG in one eye and OHT in the fellow eye is acceptable.
- 5. Able, in the opinion of the Investigator, to safely discontinue use of ocular hypotensive medications, if applicable, and undergo the appropriate required washout period for ocular hypotensive medications prior to Visit 3/Qualification/Baseline.
- 6. At Visit 3/Qualification/Baseline, at least one eye must have unmedicated (post washout) IOP ≥ 22 and ≤ 34 mm Hg at 8:00 AM and ≥ 18 and ≤ 34 mm Hg at 10:00 AM and 4:00 PM in the same eye(s) qualifying at the Visit 3 8:00 AM time point. The IOP must be at least 22 mm Hg at each consecutive measurement at the 8:00 AM time point.
- No significant VF loss, defined as a mean deviation in either eye greater than 12 dB or a central point of fixation < 5 dB in either eye. If the VF performed at or within 90 days prior to Visit 1 does not meet study required parameters, it may be repeated (test should be prior to randomization at Visit 3/Qualification/Baseline).
- 8. Best corrected visual acuity (BCVA) of +0.6 logMAR or better in both eyes at Visit 1/Screening and Visit 3/Qualification/Baseline.
- 9. Central corneal thickness \geq 480 and \leq 600 μ m in both eyes. Pachymetry within 90 days prior to Screening is acceptable.
- 10. Shaffer gonioscopic grade \geq 3 (in at least 3 quadrants) in both eyes. Gonioscopy within 90 days prior to randomization is acceptable.

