All data generated during this study and the medical records/documents from which they originated are subject to inspection by the Sponsor or designee, the FDA, and other regulatory agencies. The Investigator must notify the Sponsor or designee promptly of any inspections scheduled by regulatory authorities.

Upon completion of the study, the clinical monitor will conduct a final visit (closeout) to the site. The objectives of this visit are to ascertain that all regulatory records and reports are complete, verify that the investigational product (IP) and other supplies have been accounted for (returned/destroyed), and ensure that the Investigators are aware of their responsibilities once the study ends.

The Investigator is responsible for permitting the Sponsor or designee direct access to any study documents for monitoring and auditing purposes, for providing adequate space for monitoring, and for addressing any questions or issues that might be raised by the monitor or auditor on a timely basis.

13.6. **Case Report Forms and Study Records**

Data relating to study procedures may be entered by site personnel directly onto eCRFs available in the study's eDC system. When the eCRF is the first place study data are recorded, it will be the source document; exceptions are detailed in the Study Manual. Paper source documents will be retained at the study site when appropriate.

13.7. **Protocol Deviations**

The Investigator should not deviate from the requirements of this protocol except in the event of a medical emergency.

A major protocol deviation is defined as nonadherence to the protocol that involves inclusion/exclusion criteria, affects subject safety, or has the potential to affect the integrity of the data, for example, enrollment of a subject who does not meet key eligibility criteria, or failing to collect data necessary to interpret primary endpoints. All protocol deviations will be reported to the Sponsor by entering the event in the appropriate eCRF page. Protocol deviations should be reported to the IRB in accordance with IRB-specific guidelines. If there is any question as to whether the deviation is reportable, the Sponsor or designee and the IRB should be contacted. If subjects are enrolled in error they may be removed after review by the Medical Monitor, but removal is not required. Major and minor protocol deviations will be defined before unmasking.

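### Protocol 9.4.6 words its visual-field exclusion so that, taken numerically, the mean-deviation part bars subjects with little or no loss and passes those with loss of 12 dB or more

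*Protocol*

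**What the plan says.** Protocol 9.4.6 (Visual Field Testing) bars subjects whose field loss is functionally significant and gives two tests for this, applied to each eye. The first concerns MD: "defined as mean deviation greater than -12 dB". The second is a central fixation value below 5 dB. On equipment it says: "The preferred equipment for the VF is the Humphrey Perimeter". It also lets sites use other instruments if the sponsor approves.

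Inclusion criterion 7 in Protocol 7.1 reads: "No significant VF loss, defined as a mean deviation in either eye greater than 12 dB or a central point of fixation < 5 dB", again for either eye. The synopsis copy begins "No significant visual field (VF) loss, defined as a mean deviation in either eye greater than". In the supplied text the line breaks there, and 12 dB follows on the next line without a sign.

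The exclusion list in Protocol 7.2 has no VF criterion. SAP 5.2 refers back to the protocol for eligibility. Neither document says whether MD is recorded as negative or positive when there is loss.

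Protocol 13.7 states: "A major protocol deviation is defined as nonadherence to the protocol that involves inclusion/exclusion criteria". Protocol 11.3.1.2 and SAP 7.1.2 restrict the per-protocol (PP) population to subjects without major deviations and base the primary efficacy analysis on it.

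**The concern.** The rule in 9.4.6 names a group with significant loss and then defines it by an inequality that, read as arithmetic, selects the opposite group. Protocol section 4 describes ocular hypertension (OHT) as raised pressure without VF deficits. Subjects with OHT, one of the two target diagnoses, would therefore meet the literal exclusion.

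Three uses depend on the rule being clear:

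- **Washout.** Protocol 10.1.1 has eligibility reviewed at the end of screening, after which eligible subjects start the washout their medication requires. The minimum is 28 days for some drug classes (Protocol 10.2).
- **Repeat testing.** The protocol lets a field that does not meet study parameters be repeated before randomization, so a site must know which fields fail.
- **PP membership.** An eligibility breach counts as a major deviation. Whoever judges it needs one text to judge against.

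**Working it through.** No sample size, power or error rate is involved. The check evaluates each inequality at example MD values.

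**Inputs**
- Protocol 9.4.6: excluded if MD > -12 dB.
- Protocol 7.1 criterion 7, as supplied: not eligible if MD > 12 dB.
- Criterion 7 if a minus sign was lost: not eligible if MD > -12 dB.
- The central fixation part (below 5 dB) agrees in all three places and is set aside here.

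**Convention A: loss is negative** (an assumption, implied by the minus sign in 9.4.6)

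| MD (dB) | 9.4.6: MD > -12? | 7.1 as supplied: MD > 12? | 7.1 with minus restored: MD > -12? |
|---|---|---|---|
| 0 | yes, excluded | no, passes | yes, excluded |
| -2 | yes, excluded | no, passes | yes, excluded |
| -11 | yes, excluded | no, passes | yes, excluded |
| -12 | no, passes | no, passes | no, passes |
| -13 | no, passes | no, passes | no, passes |
| -20 | no, passes | no, passes | no, passes |

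Under 9.4.6, everyone with loss smaller than 12 dB is excluded, and everyone with loss of 12 dB or more passes on MD. Criterion 7 as supplied excludes essentially nobody on MD. With a minus restored, it has the same reversed direction as 9.4.6.

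**Convention B: loss is positive (a magnitude)**
- Criterion 7 as supplied: 13 > 12 and 20 > 12 are true, so both are barred; 0, 2 and 11 are not above 12 and pass. This matches its label.
- 9.4.6: 0, 2, 11, 13 and 20 all exceed -12, so virtually everyone is excluded.

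No single convention makes the supplied wording of criterion 7 and 9.4.6 agree with each other and with their labels. If a minus was lost from criterion 7, the two agree with each other, but under Convention A both contradict their labels.

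**The case against.** Five points can be made on the other side.

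- **The sign conflict may not exist.** A reader might infer that 7.1 and 9.4.6 carry opposite signs. The supplied text cannot establish this. Criterion 7 has lost its item number in both copies, and the synopsis breaks just before 12 dB, so a minus sign may have been lost in the same way. This stands, and the sign conflict should not be asserted. It does not rescue 9.4.6, where the sign is present.
- **The label explains the wording.** What is being defined is loss, and greater can be taken to mean a larger loss. Read literally, the rule would bar OHT subjects whom the trial is built to enrol, so sites are unlikely to apply it that way. This largely stands and limits the practical effect. It does not help a numeric check or a deviation reviewer, who needs a sign and a direction.
- **Section 9.4.6 is not the operative list.** Protocol 8.2 points to section 7 for eligibility, and 9.4.6 refers to a Study Manual that is not among the documents. True, but 9.4.6 itself says who is excluded, and section 7 is either unsigned or reversed in the same way.
- **Severe loss is not simply let in.** A reader might infer that it is. The reversal affects the MD part only. The fixation part and the exclusion for a cup-to-disc ratio above 0.8 would still bar some of these subjects.
- **A breach does not automatically remove a subject from the PP set.** SAP 8.2 says that major deviations may lead to removal, after a masked sponsor review completed before database lock. This stands. Because that review is masked, the documents give no route from this wording to between-arm bias.

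**Conclusion.** The MD definition in Protocol 9.4.6 is wrong as written. With loss recorded as negative, it captures subjects with little or no loss and, on the MD part only, leaves out those with loss of 12 dB or more. Whether criterion 7 truly conflicts with it cannot be verified from the supplied text; if a minus sign was lost there, the same reversal applies.

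The effect is probably limited, because the label shows the intended direction fairly clearly. The number of subjects affected cannot be estimated: it depends on how many sites or programmed checks apply the text literally, which the documents do not give. The point still deserves correction, because it concerns an eligibility threshold applied before washout and a breach may cost a subject a place in the primary analysis set.

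The conclusion rests on one assumption, that negative MD means loss. Under the opposite convention 9.4.6 still fails, since it would exclude virtually everyone.

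**What to change.** Reconcile the synopsis, Protocol 7.1 criterion 7 and Protocol 9.4.6 to one statement that gives the sign, the direction (in words such as worse than, or with an inequality symbol) and the MD convention. State the convention for any other perimeter the sponsor approves as well as for the preferred instrument. Check the source file of criterion 7 for a lost minus sign at the same time. The sponsor must confirm the intended rule; this review does not propose a threshold.

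Use the same statement in any eCRF check on MD and in the masked deviation review under SAP 8.2. The cost is a one-line protocol clarification and a review of the eCRF checks.
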